## 1 PROTOCOL SYNOPSIS

**Population:** Healthy adults

**Total number of participants:** 100

### 1.1 Inclusion Criteria

1. Male or female between 20 and 65 years of age, inclusive
2. BMI from 25.0 to 29.9 kg/m^2, inclusive
3. Female participants are not of child-bearing potential, defined as females who have undergone a sterilization procedure (e.g. hysterectomy, bilateral oophorectomy, bilateral tubal ligation, complete endometrial ablation) or have been post-menopausal (natural or surgically) for at least 1 year prior to screening

Or,

Females of child-bearing potential must have a negative baseline urine pregnancy test and agree to use a medically approved method of birth control for the duration of the study. All hormonal birth control must have been in use for a minimum of three months. Acceptable methods of birth control include:

- Hormonal contraceptives including oral contraceptives, hormone birth control patch (Ortho Evra), vaginal contraceptive ring (NuvaRing), injectable contraceptives (Depo-Provera, Lunelle), or hormone implant (Norplant System)
- Double-barrier method
- Intrauterine devices
- Non-heterosexual lifestyle or agrees to use contraception if planning on changing to heterosexual partner(s)
- Vasectomy of partner at least 6 months prior to screening

4. Self-reported stable body weight for the past 3 months defined as not having gained or lost more than 5 kg of body weight throughout the 3 months prior to baseline
5. Participants with the following body fat percentages:
  - Female:  $\geq 25\%$  as determined by Bioelectrical Impedance Analysis (BIA) at screening and confirmed  $\geq 30\%$  by Dual-Energy X-Ray Absorptiometry (DXA) at baseline
  - Male:  $\geq 15\%$  as determined by BIA at screening and confirmed  $\geq 20\%$  by DXA at baseline
6. Agrees to follow the diet and exercise guidelines for the duration of the study
7. Willingness to complete questionnaires, records, and diaries associated with the study, to complete all clinic visits, and provide stool samples
8. Provide voluntary, written, informed consent to participate in the study
9. Healthy as determined by medical history, laboratory results and physical exam as assessed by the Qualified Investigator (QI)

### 1.2 Exclusion Criteria

1. Women who are pregnant, breastfeeding, or planning to become pregnant during the trial

2. Allergy, sensitivity, or intolerance to the investigational product's active or inactive ingredients
3. Clinically significant abnormal laboratory results at screening as assessed by the QI
4. Current or history of any significant gastrointestinal disease requiring medication (e.g. GERD, gastroenteritis)
5. Irregular sleep schedule
6. Chronic diarrhea or constipation
7. Participants with hypertension and are on antihypertensive medication
8. Type I or Type II diabetes
9. Participants with hyperlipidemia and are on medication
10. Self-reported sleep apnea
11. Self-reported current or pre-existing thyroid condition. Treatment on a stable dose of medication for at least 3 months will be considered by the QI
12. Unstable metabolic disease or chronic diseases as assessed by the QI
13. History of or current diagnosis with kidney and/or liver diseases as assessed by the QI on a case-by-case basis, with the exception of history of kidney stones in participants who are symptom-free for 6 months
14. Significant cardiovascular event in the past 6 months. Participants with no significant cardiovascular event on stable medication may be included after assessment by the QI on a case by case basis
15. Major surgery in the past 3 months or individuals who have planned surgery during the trial period. Participants with minor surgery will be considered on a case-by-case basis by the QI
16. Cancer, except skin cancers completely excised with no chemotherapy or radiation with a follow up that is negative. Volunteers with cancer in full remission for more than five years after diagnosis are acceptable
17. Individuals with an autoimmune disease or are immune-compromised
18. Self-reported HIV-, Hepatitis B- and/or C-positive diagnosis
19. Blood/bleeding disorders as determined by laboratory results
20. Self-reported mental or neuropsychological condition and/or cognitive impairment that, in the QI's opinion, could interfere with study participation
21. Metal implants that may affect the DXA scan results will be assessed on a case-by-case basis by the QI.
22. Current use of prescribed medications listed in Section Prescribed Medications 7.3.1
23. Current use of over-the-counter medications, supplements, foods and/or drinks listed in Section 7.3.2
24. Use of cannabinoid products within 60 days of baseline. History of cannabis used will be assessed on a case by case basis by the QI
25. Use of tobacco products within 60 days of baseline
26. Self-reported alcohol or drug abuse within the last 12 months
27. High alcohol intake (average of > 2 standard drinks per day or > 10 per week)
28. Current employment that calls for shift work or have worked shift work in the last 3 weeks
29. Participation in other clinical research trials 30 days prior to screening
30. Blood donation 30 days prior to screening, during the study, or a planned donation within 30-days of the last study visit
31. Individuals who are unable to give informed consent

Protocol 20BWHM:

A randomized, double-blind, placebo-controlled study to investigate the effects of a *Bifidobacterium breve* strain on fat loss in healthy adults

32. Any other condition, that, in the opinion of the QI, may adversely affect the participant's ability to complete the study or its measures, or which may pose a significant risk to the participant

### 1.3 Schedule of Assessments

Procedures/assessments	Visit 1 Screen (Week -6)	Run-in Period Compliance Calls	Visit 2 Week 0	Visit 3 Week 6	Visit 4 Week 12
Informed consent	X				
Review inclusion/exclusion criteria	X		X		
Review medical history	X				
Review daily exercise habits	X				
Review concomitant therapies	X		X	X	X
Biometrics: Height*, weight, waist and hip circumference, heart rate, blood pressure, respiratory rate, and temperature	X		X	X	X
*only be measured at Visit 1					
Urine pregnancy test	X		X		
Physical examination			X		
Randomization			X		
CBC, Na, K, Cl, Fe, Mg, Ca, phosphate, HbA1c, fasting glucose, eGFR, creatinine, BUN, AST, ALT, GGT, ALP, TSH* and total bilirubin	X		X		X
*only be measured at Visit 1					
Blood Collection: lipid profile and fasting insulin	X		X		X
Urinalysis	X		X		X
DXA			X		X
BIA	X		X		
Stool Collection Kits Dispensed	X			X	
Stool Collection Kit Returned			X		X
Exercise Guideline Review	X	X	X	X	
Daily Bowel Habits Diary Dispensed	X		X	X	
Daily Bowel Habits Diary Returned			X	X	X
3DFR Dispensed	X		X	X	
3DFR Returned			X	X	X
Exercise Diary Dispensed	X		X	X	
Exercise Diary Returned			X	X	X
Subject Diary Dispensed	X		X	X	
Subject Diary Returned			X	X	X
Placebo Dispensed		X			
Placebo Returned			X		
IP Dispensed			X	X	

Procedures/assessments	Visit 1 Screen (Week -6)	Run-in Period Compliance Calls	Visit 2 Week 0	Visit 3 Week 6	Visit 4 Week 12
IP Returned				X	X
Compliance Calculated			X	X	X
Adverse Events		X	X	X	X

## 2 LIST OF ABBREVIATIONS

3DFR	Three-Day Food Record
AE	Adverse Event
ALP	Alkaline phosphatase
ALT	Alanine Aminotransferase
AST	Aspartate Aminotransferase
BIA	Bioelectrical impedance analysis
BMI	Body Mass Index
BP	blood pressure
BUN	Blood urea nitrogen
Ca	Calcium
CBC	Complete Blood Count
CRF	Case Report Form
Cl	Chloride
DXA	Dual-Energy X-Ray Absorptiometry
EDTA	Ethylenediaminetetraacetic Acid
eGFR	Glomerular Filtration Rate
etc.	“and so forth”
e.g.	“for example”
et al	“and others”
EOS	End of the Study
F/B	Firmicutes/Bacteroidetes
Fe	Iron
g	Gram
GCP	Good Clinical Practice
GGT	Gamma-glutamyl transferase
HbA1c	hemoglobin A1c
HDL-C	High-density lipoprotein cholesterol
HR	Heart Rate
ICF	Informed Consent Form
ICH	International Conference of Harmonization
IP	Investigational product
ITT	Intent to Treat
IRB	Institutional Review Board
K	Potassium
kg	Kilogram
LDL-C	Low-density lipoprotein cholesterol
MCH	Mean Corpuscular Hemoglobin
MCHC	Mean Corpuscular Hemoglobin Concentration
MCV	Mean Corpuscular Volume
MPV	Mean Platelet Volume
Mg	Magnesium
Na	Sodium
NEFA	non-esterified fatty acids
NSAIDs	non-steroidal anti-inflammatory drugs
OTC	over-the-counter

PP	Per protocol
PPIs	Proton Pump Inhibitors
QI	Qualified Investigator
RBC	Red Blood Cells
RDW	Red Blood Cell Distribution Width
SAE	Serious Adverse Event
SOP	Standard operating procedure
SST	Serum Separating Tube
SSRI	Selective serotonin reuptake inhibitors
TG	Triglyceride
TPD	Therapeutics Products Directorate
TSH	Thyroid stimulating hormone
ULN	Upper limit of normal
VLDL	very-low-density lipoprotein
WBC	White Blood Cell
WHO	World Health Organization

#### 4 INTRODUCTION

In 2016, 1.9 billion adults or 39% of the world's population were classified as overweight (body mass index (BMI) of 25.0 to 29.9 kg/m^2) by the World Health Organization (WHO) (1). Overweight has become a critical issue in North America, with the prevalence of obesity highest in middle-aged adults (2). In the United States (US), the prevalence of overweight and obesity were estimated at 71.6% of the total population in 2015-2016 (3). Consequently, weight loss market value has been increasing, with the US weight loss market worth approximately \$72 billion (4). This value is expected to rise as the population becomes more health-conscious and aware of the risks associated with excess body weight.

In early adulthood, excess body weight is a risk factor associated with several health complications later on in life, including type II diabetes, cardiovascular disease, and non-alcoholic fatty liver disease (5, 6). Excess weight gain influences several pathways in the body, altering circulating lipids, glucose, insulin, hemoglobin A1c (HbA1c) levels, and liver function. Increases in visceral adipose tissue lead to a rise in the production of non-esterified fatty acids (NEFA), which decreases insulin sensitivity and play a role in the development of insulin resistance (6). As a result, glucose uptake by muscle tissue is decreased while free fatty acid and glucose production by adipose tissue and liver are increased, respectively (7). These altered pathways increase very-low-density lipoprotein (VLDL) and triglyceride (TG) production in the liver; inducing a decrease in high-density lipoprotein cholesterol (HDL-C) and increase in low-density lipoprotein cholesterol (LDL-C) and apolipoprotein B (8). Additionally, insulin resistance indirectly contributes to the VLDL concentration by lowering lipoprotein lipase activity (7).

Probiotics have been used for decades for maintaining intestinal health, and in recent years probiotics have been proposed for weight management. Previous studies reported a correlation between weight and gut *Bifidobacterium* abundance, showing that the level of *bifidobacterium* in the gut microbiota was lower in obese people (9). *Bifidobacterium breve* (*B. breve*) is a probiotic strain known for its beneficial functions in weight management (10, 11). It has been shown to improve intestinal barrier function, upregulate fat metabolism, and mitigate systemic inflammation (10, 12, 13).

Several studies have also demonstrated that *B. breve* may improve parameters associated with obesity. Supplementation with *B. breve* in obese mice was shown to reduce visceral fat gain and to lower serum cholesterol, glucose, and insulin compared to the control group (14). In a randomized, double-blind, placebo-controlled trial, healthy adults consuming a high-fat diet supplemented with a probiotic mix containing *B. breve* had reductions in body weight and fat mass after 4 weeks of supplementation (15). In another randomized placebo-controlled trial overweight adults were supplemented with *B. breve* for 12 weeks. Results from the study showed significantly lower fat mass along with improvements in liver function and inflammatory markers such as  $\gamma$ -glutamyl transpeptidase (GGT) and high-sensitivity C-reactive protein (CRP) compared to the placebo group (10, 11).

Despite the promising results of probiotics and reductions in body weight and fat mass, weight management is multifactorial and sustained weight loss often has a low success rate. In conjunction with dietary intervention, regular exercise has been proposed to improve body composition, intestinal microbiota diversity, and digestion (16, 17). However, prolonged exercise may disrupt the gastrointestinal tract and reduce the abundance of beneficial bacteria (17). To counteract this effect, the use of probiotics combined with exercise intervention has been proposed for effectively managing weight loss. The combination of aerobic exercise and administration of probiotics has been examined in several clinical trials and it was found that the combination was effective in improving body composition and inflammatory responses (18-20).

## Protocol 20BWHM:

A randomized, double-blind, placebo-controlled study to investigate the effects of a *Bifidobacterium breve* strain on fat loss in healthy adults

The gut microbiota composition influences the effects of foods and drugs. It is reported that individuals who improved their glucose tolerance by taking barley kernel-based bread (responders) had a higher Prevotella/Bacteroides ratio as compared with individuals who did not (non-responders) (21). Several clinical studies indicate that the gut microbiota affects the therapeutic efficacy of checkpoint blockade immunotherapy (22). It is assumed that changes in microbial composition are associated with the anti-obesity effects of *B. breve*.

This study is a randomized, placebo-controlled, clinical trial investigating the effect of *Bifidobacterium breve* supplementation with exercise intervention on fat loss. Participants will be healthy adults between the ages of 20 and 65 with a Body Mass Index (BMI) from 25 to 29.9 kg/m^2.

## 5 STUDY OBJECTIVES

The objective of this study is to investigate the effect of *Bifidobacterium breve* on fat loss in healthy adults.

### Primary outcome:

The difference in change in fat loss from baseline (% or g), as assessed by Dual-Energy X-Ray Absorptiometry (DXA), between *B. breve* and placebo after 12 weeks of supplementation.

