### Secondary outcomes:

The difference in change from baseline between *B. breve* and placebo in:

1. Body composition (weight, BMI, android/gynoid fat ratio, and muscle mass (% or g) as assessed by DXA after 12 weeks of supplementation
2. Waist circumference, hip circumference, and waist/hip circumference ratio after 6 and 12 weeks of supplementation
3. Lipid profile (total cholesterol, HDL-cholesterol, LDL-cholesterol, triglycerides) after 12 weeks of supplementation
4. Biomarkers of glycemic control (fasting blood glucose, HbA1c, fasting insulin levels) after 12 weeks of supplementation
5. Liver markers (aspartate transaminase (AST), alanine aminotransferase (ALT), gamma-glutamyl transferase (GGT), and alkaline phosphatase (ALP)) after 12 weeks of supplementation
6. Frequency of bowel movements after 6 and 12 weeks of supplementation
7. Body composition (weight, BMI, total body fat (% or g), android fat (% or g), gynoid fat (% or g), android/gynoid fat ratio, and muscle mass (% or g) and waist circumference, hip circumference, and waist/hip circumference ratio) in participant groups classified by microbiota composition at week 0
8. Microbiota composition analysis

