## **10.8 Dual-Energy X-Ray Absorptiometry (DXA) Scan**

The Dual-Energy X-Ray Absorptiometry Scan will be conducted at KGK clinic (London, ON) at visits 2 (week 0), and 4 (week 12) by trained technicians. Body tissue density will be measured by a form of X-ray radiation and converted into body fat and muscle mass percentage for assessment. Prior to the day of the DXA assessment, the coordinators will remind the participants to limit the amount of water and food consumption accordingly. A full body composition DXA scan will expose the participant to a total dose of <10uSV, depending on the size of the participant. This amount is less than a person is exposed to on an east to west coast flight within the USA and similar to the normal background radiation received over the course of a single day level (23, 24).

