## 12 STATISTICAL EVALUATION

### 12.1 Determination of Sample Size

With a total sample size of 100 (50 per group; 40 completers), it is possible to detect a difference in mean change in percent body fat or body fat mass of 0.76% or 0.79 kg respectively, in a parallel design at a two-sided unadjusted 5% significance level, 80% power and 20% attrition rate. This calculation is based on standard deviations of 1.19% and 1.24 kg for percent body fat and body fat mass respectively, estimated from a study by Minami et al (2018).

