### 12.3 Statistical Analysis Plan

For each continuous endpoint including percent body fat, body fat mass, visceral fat area, weight, BMI, total cholesterol, HDL-cholesterol, LDL-cholesterol, triglycerides, waist circumference, and hip circumference, fasting blood glucose, HbA1c, fasting insulin levels, AST, ALT, GGT, ALP, a summary table will be prepared with a variety of summary statistics including mean, standard deviation, median, min-max range and number of participants analyzed for each time point-treatment pairing. These data will be classified in subgroups based on the similarity of microbiota composition.

To account for any a priori differences between groups, the similar summary statistics of the changes from baseline will also be provided. Mean values will be displayed as graphs, with a separate line for each product, and error bars indicating  $\pm$  SEM. Mean changes from baseline will also be graphed similarly. Changes in continuous endpoints from screening/baseline will be calculated as:

$$\text{Change to } V_i = \text{Value at } V_i - \text{Value at } V_{\text{screening/baseline}}$$

Continuous variables will be tested for normality and log-normality using histograms, box plots and Q-Q plots. Log-normally distributed variables will be analyzed in the logarithmic domain. Summary statistics will be provided as non-transformed values. Intractably non-normal variables will be analyzed by appropriate non-parametric tests.

Protocol 20BWHM:

A randomized, double-blind, placebo-controlled study to investigate the effects of a *Bifidobacterium breve* strain on fat loss in healthy adults

The primary endpoint - change in fat loss from baseline (%) or g), as assessed by Dual-Energy X-Ray Absorptiometry (DXA), between *B. breve* and placebo after 12 weeks of supplementation - will be assessed for between-group differences using ANCOVA, with the baseline measurements as covariate.

Continuous secondary endpoints will be tested for between-group differences using repeated measures linear mixed-effects ANCOVA. This will allow for the random effects associated with each subject to be accounted for. The dependent variable will be the change at each visit, the fixed effects will be the study group \* visit number, and the covariate will be the dependant variable at baseline (Day 0).

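### The primary outcome is DXA fat change in percent or grams; the plan never says which variable decides the trial or how a split result is judged

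*Protocol*

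**What the plan says.** The primary outcome in protocol section 5 is "The difference in change in fat loss from baseline (% or g), as assessed by Dual-Energy X-Ray Absorptiometry (DXA"), compared between arms at week 12. Protocol 12.3, SAP section 2 and the outcome table in SAP 5.1 keep the same percent-or-grams alternative.

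Elsewhere the protocol treats these as two variables. Section 12.1 says "it is possible to detect a difference in mean change in percent body fat or body fat mass of 0.76% or 0.79 kg respectively", using SDs of 1.19% and 1.24 kg, at a "two-sided unadjusted 5% significance level". Section 12.3 opens its endpoint list with both: "For each continuous endpoint including percent body fat, body fat mass, visceral fat area, weight, BMI". It plans summaries and graphs for every listed endpoint, and "similar summary statistics of the changes from baseline will also be provided".

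The primary endpoint "will be assessed for between-group differences using ANCOVA, with the baseline measurements as covariate" (protocol 12.3). SAP 5.1 states one null hypothesis, on fat loss with no scale, and one ANCOVA on the change at week 12. SAP 4.4 gives only the 5% significance level.

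Protocol 10.8 says the scan is "converted into body fat and muscle mass percentage for assessment", but does not make the percentage the deciding variable. Secondary outcome 1 is "Body composition (weight, BMI, android/gynoid fat ratio, and muscle mass (% or g) as assessed by DXA after 12 weeks of supplementation"; total fat is not in it. Secondary outcome 7 includes total fat, but only within microbiota groups, and SAP 5.2 defers outcome 7 to a separate SAP.

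**The concern.** The primary ANCOVA cannot be programmed from these documents, because its dependent variable is not fixed. Percent and grams are not two units for one quantity. Percent body fat also moves when lean mass changes, and everyone in this trial follows an exercise programme, with muscle mass a secondary outcome. The two tests can therefore disagree.

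If they do, the plan does not say whether the trial met its primary outcome. The wording also leaves room for two unadjusted primary tests, or for choosing the scale after results are seen. Either would take the false-positive rate of the primary claim above 5%. The measure not chosen has no assigned between-group test in the whole trial, so its place in the report is undefined as well.

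**Working it through.** **Inputs.** From protocol 12.1: 50 per arm, 40 completers per arm, two-sided 5%, 80% power, 20% attrition; percent body fat difference 0.76 with SD 1.19; fat mass difference 0.79 kg with SD 1.24 kg. The correlation r between the two test statistics is not in the documents, so it is varied from 0.70 to 0.99. Both measures come from the same scan, so I regard the high values as more plausible.

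**Step 1: reproduce the plan's figures.** The noncentrality is Δ / (SD × √(2/n)), and √(2/40) = 0.2236.

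- Percent body fat: 0.76 / (1.19 × 0.2236) = 2.856. Two-sample t-test power is 80.5%, and the difference detectable at 80% power is 0.755.
- Fat mass: 0.79 / (1.24 × 0.2236) = 2.849. Power is 80.3%, and the detectable difference is 0.787 kg.
- Attrition: 40 / (1 − 0.20) = 50 per arm, 100 in total.

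The stated figures hold for each variable taken alone. The standardized effects are almost equal (0.76/1.19 = 0.639; 0.79/1.24 = 0.637), so the sample size does not reveal which variable was meant as primary.

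**Step 2: two tests together.** Treat the two statistics as bivariate normal with correlation r and critical value 1.96. Single-measure power is then p₁ = 81.5% and p₂ = 81.3%. With E = P(at least one significant):

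- P(both) = p₁ + p₂ − E
- P(exactly one) = 2E − p₁ − p₂

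Under the null, p₁ = p₂ = 5% and E is the false-positive rate of an either-wins rule.

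| r | Null: E | Stated effects: E | Both | Exactly one |
|---|---|---|---|---|
| 0.70 | 8.3% | 89.7% | 73.1% | 16.6% |
| 0.80 | 7.8% | 88.2% | 74.6% | 13.6% |
| 0.90 | 7.0% | 86.2% | 76.6% | 9.6% |
| 0.95 | 6.5% | 84.8% | 78.0% | 6.8% |
| 0.99 | 5.7% | 82.9% | 79.9% | 3.0% |

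Under the null, exactly one is significant in 2 × 5.66% − 10% = 1.3% of trials at r = 0.99, and in 2 × 8.35% − 10% = 6.7% at r = 0.70.

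**Step 3: check with t tests.** A simulation of 100,000 trials per value of r, 40 per arm, agrees. From r = 0.70 to 0.99, exactly one is significant in 17.2% down to 3.1% of trials, and the either-wins error falls from 8.4% to 5.6%. Power is 89.1% down to 82.1% for either and 71.9% up to 79.0% for both.

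**Limit.** These are unadjusted comparisons of 40 completers per arm, as in protocol 12.1. The planned test is a baseline-adjusted ANCOVA, and missing values are imputed, so the analysed number could exceed 40.

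**The case against.** The percent-or-grams notation may be only a reporting convention. It is also used for muscle mass and regional fat, and since both fat measures are powered and summarised, a natural reading is that both will be reported. That would make selective reporting less likely. It would not say which one decides, or what a split result means.

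The computed harm is also conditional. No sentence says that success on either measure is enough. The split rates assume that both true effects equal the detectable differences. If the correlation is 0.95 to 0.99, the excess error is only 1.5 to 0.7 points and splits occur in about 7% to 3% of trials. All of this stands, so the case rests on the missing decision rule rather than on the size of the inflation.

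Two further points are fair. The measure not chosen is not wholly without tests: protocol 12.3 plans baseline and within-group comparisons for continuous variables. And naming one variable is not the only valid repair, as requiring both or splitting alpha would also close the gap, at a price given under the fix.

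**Conclusion.** The concern holds and must be fixed before the analysis. No passage in either document names the deciding variable or judges a split result, and the SAP repeats the protocol's alternative instead of resolving it. This does not depend on the correlation: the only primary claim lacks a defined dependent variable, and a choice made after results are seen could not be credibly defended.

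The size does depend on assumptions. For r from 0.99 to 0.70, and if both stated effects are true, the plan would have no verdict in 3.0% to 16.6% of trials. The false-positive rate of 5.7% to 8.3% applies only if either measure could count. The lower end of each range is the more plausible.

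**What to change.** Before outcome data by group, coded or unblinded, reach the statistician (protocol 15.3 sends a blinded soft-lock copy for analysis):

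- Name either percent body fat or fat mass as the sole primary outcome in protocol 5 and 12.3 and in SAP 2 and 5.1, tested by the stated ANCOVA at two-sided 5%.
- Add the other to secondary outcome 1 as a whole-trial comparison (protocol 5, SAP 2.1 and 5.2). Testing it only if the primary is significant is optional.
- Mark in protocol 12.1 which detectable difference belongs to the primary. The other line may stay.

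The cost is a change of wording. N=100 and the stated 80% power stand whichever variable is named. Compared with an either-wins reading, which the plan does not state, t-test power at the stated effects falls from about 82% (r = 0.99) or 89% (r = 0.70) to 80.3–80.5%. At r = 0.99 that is less than 2 points.

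The alternatives cost more. Requiring both measures gives about 79% (r = 0.99) to 72% (r = 0.70) power by t tests with 40 per arm. Splitting alpha at 2.5% each needs 47 completers per arm (normal approximation). Then 47 / 0.80 = 58.75, so 59 per arm are randomized, 118 in total.

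This settles the variable only. The t-test or Wilcoxon test that SAP 5.1 places beside the ANCOVA is a separate point.
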